6.1. Summary of assessments

Figure 2. Assessments planned for acute TBI patients

		TRI	AL PERIOD	
	Enrolment	Initial assessment (may be at enrolment)	Post-allocation (monitoring interval clinically determined)	Close-out
TIMEPOINT**	-t1	Contact 1 (0-14 days post head injury or at enrolment)	Contact 2-5 (1, 3, 6 and 9 months after head injury or enrolment)	Contact 6 (12 months after head injury)
ENROLMENT:				
Eligibility screen	Х			
Informed consent	Х			
ASSESSMENTS:				
Collect blood and saliva		X (face to face)	X (1 and 6 months only, face to face)	X (face to face)
Visual function tests (e.g. visual acuity and field tests, optical coherence tomography (OCT), OCT angiography, pupillometry, Email saccadic latency and autorefraction.		X (face to face)	X (1 and 6 months only, face to face)	X (face to face)
Mental health outcomes (social and occupational functioning assessment)		X (face to face and remotely)	X (1 and 6 months only, face to face and remotely)	X (face to face or remotely)
Self-reported measures collected by post (e.g. BIVSS (visual impairment, General anxiety disorder, PTSD, Suicidal behaviour, alcohol use and quality of life		X (all collected remotely)	X (1, 3, 6 and 9 months, all collected remotely)	X (all collected remotely)
Head injury outcome				х

Study name:	Fraumatic brain injury related changes in military veterans					
Protocol version number:	3.0	version date:	11 October 2023	Page:	13 of 22	

		TRI	AL PERIOD	
	Enrolment	Initial assessment (may be at enrolment)	Post-allocation (monitoring interval clinically determined)	Close-out
TIMEPOINT**	- t 1	Contact 1 (at enrolment)	Contact 2-4 (3, 6 and 9 months enrolment)	Contact 5 (12 months after enrolment)
ENROLMENT:				
Eligibility screen	Х			
Informed consent	Х			
ASSESSMENTS:				
Collect blood and saliva		X (face to face)	X (at 6 months only, face to face)	X (face to face)
Visual function tests (e.g. visual acuity and field tests, optical coherence tomography (OCT), OCT angiography, pupillometry, Email saccadic latency and autorefraction.		X (face to face)	X (at 6 months only, face to face)	X (face to face)
Mental health outcomes (social and occupational functioning assessment)		X (face to face and remotely)	X (at 6 months only, face to face or remotely)	X face to face or remotely)
Self-reported measures collected by post (e.g. BIVSS (visual impairment, General anxiety disorder, PTSD, Suicidal behaviour, alcohol use and quality of life		X (all collected remotely)	X (at 3, 6 and 9 months, all collected remotely)	X (all collected remotely
Head injury outcome				Х

Figure 3. Assessments planned for military veterans group

Study name:	Traumatic brain injury related changes in military veterans					
Protocol version number:	3.0	version date:	11 October 2023	Page:	14 of 22	

-igure 4. Assessments pl		,,,,,,,,,,,,,,,,,,,,,,,,,,,,,,,,,,,,,,,	AL PERIOD	
	Enrolment	Initial assessment (may be at enrolment)	Post-allocation	
TIMEPOINT**		Contact 1 (single assessment point)	Contact 2 (6 months after enrolment)	
ENROLMENT:				
Eligibility screen		Х		
Informed consent		Х		
ASSESSMENTS:				
Collect blood and saliva		X (face to face)	X (face to face)	
Visual function tests (e.g. visual acuity and field tests, optical coherence tomography (OCT), OCT angiography, pupillometry, Email saccadic latency and autorefraction		X (face to face)	X (face to face)	
Mental health outcomes (social and occupational functioning assessment)		X (face to face and remotely)	X (face to face or remotely)	
Self-reported measures collected by post (e.g. BIVSS (visual impairment, General anxiety disorder, PTSD, Suicidal behaviour, alcohol use and quality of life		X (all collected remotely)	X (6 months, all collected remotely)	
Head injury outcome		N/A		

Figure 4. Assessments planned for non-head injury control group

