1.2. Study Rationale

1.2.1. Justification for participant population

Military personnel are increasingly at risk of TBI during conflicts and especially exposure to blast. Severe TBI is easy to spot but over 80% of TBIs in military personnel are mild TBI (mTBI), which is characterised by short-term loss of consciousness and or altered mental state. Mild TBI has emerged as a signature injury and an important concern in both US and UK military populations, because of the potential for long term negative sequalae. Of military personnel returning from Iraq and/or Afghanistan, up to 40% of military personnel in the US had a mTBI¹⁹, whilst the prevalence in the UK cohort was smaller at around 5%²⁰ with one report suggesting that neuropsychiatric problems could affect as much as 70% of veterans²¹. However, all severities of TBI are associated with a broad range of subsequent psychiatric and neurological disorders including headache, fatigue, sleep disorder, dizziness, amnesia, information processing slowing, executive dysfunction, depression, anxiety and suicidal behaviour²². TBI sustained in combat is also accompanied by posttraumatic stress disorder (PTSD) and bodily trauma, which adds to the difficulty in determination of the relative contribution of each of these factors to eventual outcomes. Biomarkers have the potential to help identify those at risk of poor recovery which would aid deployment of early interventions.

The aim of this investigation is to evaluate candidate fluid biomarkers in blood and saliva from veterans who have suffered a TBI and correlate these with visual assessments, standard clinical assessments of mental health and patient reported outcome measures (PROMs) that assess mental health and quality of life over time. All of the data will be combined to develop a multifaceted algorithm to predict prognosis in veterans and provide pilot data to inform a larger study. The study will also identify biomarkers that can enable rapid decisions as to whether further intervention is required to prevent significant changes to qualify of life in veterans with a TBI and inform rehabilitation strategies to increase optimal management opportunities.

Study name:	Traumatic brain inju	raumatic brain injury related changes in military veterans					
Protocol version number:	3.0	version date:	11 October 2023	Page:	8 of 22		

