4.1. Inclusion Criteria for acute TBI group

- 1. Over the age of 18
- 2. Must have 2 eyes

3. Not all participants will have capacity to consent (e.g. moderate to severe TBI). For these participants, they will require a personal or nominated consultee.

- 4. Willing and able or consented by consultees to follow the protocol
- 5. Moderate or severe head injury requiring admission to the Queen Elizabeth Hospital within the prior 14 days

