4.7. Eligibility criteria for nominated consultee

- 1. Only appointed if no family member or friend is willing or able to act as a consultee
- 2. Must have no connection with the project
- 3. Capacity to consent

5. Consent

A member of the clinical care team (e.g. doctor, research nurse or practitioner) at Queen Elizabeth Hospital Birmingham will first identify potential acute TBI and control group participants to ascertain whether they are interested in participating in the study. They will be approached after either head injury for the acute TBI group (i.e. 0-14 days post-injury) or any other injury not involving the head for the control group in the inpatient ward or in clinic (outpatient) or during telephone / virtual follow up.

Veterans will be recruited through existing links with the military and as they are discharged from military care into NHS care. This includes partner site the Defence Medical Rehabilitation Centre in Stanford Hall where the clinical care team will identify suitable participants and obtain full written consent prior to participants visiting the Queen Elizabeth Hospital in Birmingham for blood/saliva collection and all tests. Veteran's will also be recruited through advertisements and direct contact with veterans' charities such as Bravo Victor and Blind Veterans UK.

Once an acute TBI or control patient or a veteran has expressed an interest in participating, and has provided full written consent to the clinical care team, they will be introduced to a member of research team (e.g. post-doctoral research fellows or assistants). A member of the research team will determine by talking to the patient and review of the patient's notes whether or not the patient is suitable to participate in the study. If the patient is not suitable for inclusion in the trial, their data will not be retained.

In addition, veterans who have already been discharged from the military will also be recruited through advertisements and direct contact with veterans' charities such as Bravo Victor and Blind Veterans UK. These patients will contact the research team if interested and a trained member will obtain full written consent prior to determining the suitability of the participant in the study.

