All investigations are routine clinical investigations or variants thereof that normally do not carry any appreciable risks of adverse events (AEs). The collection and reporting of AEs, however, will be in accordance with the UK Policy Framework for Health and Social Care Research and the requirements of the National Research Ethics Service (NRES) and Health Research Authority (HRA). Definitions of different types of AEs are listed in the table of abbreviations and definitions. The Investigator should assess the seriousness and causality (relatedness) of all AEs experienced by the study participant this should be documented in the source data with reference to the protocol. We will also follow University of Birmingham processes for safety reporting as per the Quality Management System: https://www.birmingham.ac.uk/research/activity/mds/mds-rkto/governance/qms.aspx.

8. Samples

Blood (7ml) and saliva (2-3ml) will be collected in standard tubes in the outpatients department of UHB and these volumes are routinely collected as part of standard care. Blood will be collected by the clinical care team by trained nurses/doctors. Saliva is collected by simply spitting into a special tube containing a stabiliser reagent. Needlestick injuries during blood collection are minimised by trained and competent nurses/doctors who will collect blood.

All samples will be transported by the research team and stored in labelled aliquots and in lockable, HTA compliant freezers. Samples will be transported to University of Birmingham labs and rendered acellular by centrifugation. Serum and saliva samples will then be aliquoted and stored in lockable freezers until required. Biomarkers will be detected in serum and saliva by enzyme linked immunosorbent assays (ELISA) using commercially available kits. See attached risk assessment form (COSHH human biological fluids).

After analysis, any remaining samples will be kept in locked University-owned freezers for up to 10 years or transferred to other ethically approved projects looking at serum and saliva biomarkers.

9. Data Handling and Record Keeping

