12.1. Definition of Outcome Measures

The primary outcome measure will be the longitudinal changes in mental health status and quality of life. This will be defined using parameters outlined in the clinical assessments section. The secondary outcome will be longitudinal changes in fluid biomarkers of injury (e.g. glial fibrillary acidic protein (GFAP), S100 β , tumor necrosis factor- α and myelin basic protein), visual function (e.g. visual acuity, contrast acuity, colour vision, visual field pupil reaction, focussing mechanism and eye movements, and brain injury outcomes assessed using the Glasgow outcome scale and Mayo-Portland Adaptability Inventory), other mental health status and PROMs.

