12.2. Power Calculation and Statistical Analysis

Data obtained from all clinical examinations and laboratory tests will be compared between the first visit (Contact 1) and the subsequent follow-up visits (Contact 2-6). Many of these data are continuous and normally distributed as well as being repeated measures data of the same subjects. As such, repeated measures ANOVA will be used to determine changes over time. Data that are not normally distributed or numeric will be analysed using non-parametric tests. Linear mixed models, linear regression and analysis of covariance will be used for binary and ordinal outcomes as appropriate. Trial statisticians in the Birmingham Clinical Trials Team will be engaged for further statistical advice, if required.

This is a pilot study to evaluate longitudinal changes in fluid and visual biomarkers of brain injury, mental health status and self-reported quality of life measures in patients with TBI (civilian and military veterans). The sample size is based on:

1) statistical advice that in a pilot / feasibility study, 30 subjects in each group are recommended to allow estimation of the parameters of interest³².

2) Based on Child's et al.³² which showed a difference of 5um in global retinal nerve fibre layer thickness between boxers and controls, an average RNFL thickness of 101. Past experience in the concussion clinic suggests that we are able to follow 80% of patients at the 3-month point (i.e. only 20% lost to follow up). We based the power calculation looking for power to detect a 5um change in the repeated measures, assuming correlation of 0.9 between repeated measures of RNFL thickness (conservative given that in the absence of pathology, RNFL thickness varies very little). Simulated power calculations in R revealed that 24 participants with complete data (recruiting 30 and assuming a 20% drop out) would have >80% power to detect a 2µm change in RNFL thickness and 100% power to detect a 5µm decrease.

13. Ethical Considerations

The study will be performed in accordance with the recommendations guiding physicians in biomedical research involving human subjects, adopted by the 18th World Medical Association General Assembly, Helsinki, Finland, June 1964, amended at the 48th World Medical Association General Assembly, Somerset West, Republic of South Africa, October 1996 (website: http://www.wma.net/en/30publications/10policies/b3/index.html).

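### The acute-group reference sample for fluid biomarkers may be drawn on any day from 0 to 14 after injury, with no stated allowance for time since injury, so change from Contact 1 mixes sampling day with biological change.

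*Protocol*

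**What the plan says.** - **Reference sample.** For the acute TBI group, Figure 2 in section 6.1 defines the first assessment as "Contact 1 (0-14 days post head injury or at enrolment". Section 5 gives the same approach window: "head injury for the acute TBI group (i.e. 0-14 days post-injury". Section 4.1 admits patients with "Moderate or severe head injury requiring admission to the Queen Elizabeth Hospital within the prior 14 days". No narrower time for the blood draw is given.
- **Later samples.** Figure 2 schedules blood and saliva for this group again at 1, 6 and 12 months. Contacts 2 to 5 are timed from head injury or from enrolment. Section 6.2 allows 10% either way for visits 2 to 6; Contact 1 is not covered by that tolerance.
- **Analysis.** Under section 12.2, clinical and laboratory data "will be compared between the first visit (Contact 1) and the subsequent follow-up visits (Contact 2-6", with repeated measures ANOVA for continuous, normally distributed data. The section mentions no term for days since injury.
- **Outcome.** Section 12.1 states: "The secondary outcome will be longitudinal changes in fluid biomarkers of injury", naming GFAP, S100β, TNF-α and myelin basic protein as examples.
- **Place of sampling.** Section 8 says that blood and saliva "will be collected in standard tubes in the outpatients department of UHB".

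**The concern.** A change score is only as well defined as its reference point. Here the reference point floats over two weeks. Hypothesis 2 in section 2.1 expects injury to produce detectable biomarker changes, section 1.2.2 sets out to measure them over time, and only the acute group receives an extra fluid sample at 1 month. If levels move during the first fortnight, two patients with the same biological course but different draw days enter the analysis with different baselines and therefore different changes. An ANOVA indexed by visit treats those changes as the same contrast.

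The draw day may also not be random. Section 5 describes several routes into the study: approach on the ward, in clinic or by telephone or virtual follow-up, and entry through a consultee for patients who are unconscious, who then give blood only. If route or capacity shifts the draw day, the result could be bias as well as noise. At stake are the acute-group biomarker trajectories and their correlation with later mental health and quality of life.

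**Working it through.** **The plan's own figure.** There is none to reproduce. The sample-size argument in section 12.2 rests on 30 per group and on retinal nerve fibre layer thickness (30 × 0.8 = 24 complete). No half-life, variance or power is given for any fluid biomarker.

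**Step 1: spread of intervals, from the protocol's own windows.** Take a month as 30.4 days. The 10% tolerance is about 3 days, so the 1-month visit falls between 27.4 and 33.4 days after its anchor.
- Anchored to injury: shortest interval from Contact 1 = 27.4 − 14 = 13.4 days; longest = 33.4 − 0 = 33.4 days.
- Anchored to enrolment: the 1-month sample falls between 27.4 + 0 = 27.4 and 33.4 + 14 = 47.4 days after injury.

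The reference sample therefore has a 14-day window, against about 6 days in total for the first sample compared with it.

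**Step 2: how much this could matter, under assumptions.** Assume that draw day is uniform on 0–14 and unrelated to the patient's level, with first-order decay of half-life h days. Let s be the SD of all other variation in the natural-log baseline.
- Timing SD: SD_t = (ln 2 / h) × 14/√12 = 2.80/h.
- Timing share of variance: SD_t² / (SD_t² + s²).

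| h (days) | SD_t | s = 0.5 | s = 0.8 | s = 1.5 |
|---|---|---|---|---|
| 1 | 2.80 | 97% | 93% | 78% |
| 2 | 1.40 | 89% | 75% | 47% |
| 4 | 0.70 | 66% | 43% | 18% |
| 7 | 0.40 | 39% | 20% | 7% |
| 14 | 0.20 | 14% | 6% | 2% |
| 30 | 0.09 | 3% | 1% | 0.4% |

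**Step 3: let levels settle at a background.** Use level = b × (1 + A × 2^(−t/h)), where A is the excess at injury as a multiple of background b. For s = 0.5 / 0.8 / 1.5:
- A = 10: 62% / 39% / 16% at h = 1; 66% / 43% / 18% at h = 2; 31% / 15% / 5% at h = 7.
- A = 100: 89% / 76% / 47% at h = 1.

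**Step 4: one patient, two draw days.** Assume a level 10 times background on day 0 and a return to background by 6 months: level(t) = 1 + 9 × 2^(−t/h), fall = 1 − 1/level.
- Day 0: 1 − 1/10 = 90%.
- Day 14, h = 1: level about 1.00, fall about 0%.
- Day 14, h = 3: level 1.354, fall 26%.
- Day 14, h = 7: level 3.25, fall 69%.

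The draw day alone changes the recorded size of the fall, and in this model never its direction.

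**Step 5: place of sampling.** Section 8 puts collection in the outpatients department. The acute group is defined by hospital admission (section 4.1) and may be approached on the inpatient ward (section 5). It includes unconscious patients from whom blood is taken (section 5). These statements do not fit together.

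**The case against.** Several stronger readings are tempting, and the documents do not support them.

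- **Draw day dominates the result.** A reader might infer that the outcome mostly reflects when the sample was taken. That needs half-life, peak height and between-patient spread, and the protocol gives none of them. In the tables above the share passes one half only when half-life is short and either the peak is high or other variation is small. That all the named markers rise and then clear in the same way is also not stated.
- **The whole secondary outcome is affected.** Section 12.1 also covers visual function, brain injury outcomes, other mental health status and PROMs. Veterans start at enrolment and controls have no acute window. Section 1.2.2 also plans comparisons with controls and between groups, so change from Contact 1 is not the only use of these data.
- **Severity drives draw day.** It might, but finding a consultee could delay sampling as easily as unconsciousness could advance it. The direction is open.
- **The first sample waits for discharge.** Section 8 read alone suggests this, but section 5 provides for ward approach and for blood from unconscious patients. It is a wording conflict and does not show late sampling.
- **The decision-marker aim is undermined.** The aim in section 1.2.1 to "identify biomarkers that can enable rapid decisions as to whether further intervention is required" is tied in that sentence to veterans, who have no 0–14 day window.

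It is also fair to say that this is an exploratory pilot, that section 9.1 already keeps dates of visits and tests, and that a separate analysis plan could add a covariate. These points limit the severity, but section 12.2 already fixes the comparison with Contact 1, and an analysis plan can alter neither when blood is drawn nor the wording of section 8.

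**Conclusion.** The point holds as a cheap improvement, limited to fluid biomarkers in the acute TBI group. Followed as written, the change from Contact 1 combines biological change with a draw day that can vary by 14 days, and no allowance for it is stated. The spread of 13 to 33 days between Contact 1 and the 1-month sample follows from the protocol's own windows, with visits counted from injury.

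The statistical size is not determined. It runs from under 1% to about 97% of log-baseline variance, under assumed half-lives of 1 to 30 days, other SD of 0.5 to 1.5, uniform draw days and pure decay. If actual draw days cluster, the noise is smaller. If they depend on consent route or capacity, bias is possible in a direction that the documents do not settle.

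**What to change.** 1. **Record and model time since injury.** Record date and time of injury and of the Contact 1 draw. In section 12.2, analyse acute-group biomarkers on the log scale with injury-to-sample time in the model, for example a linear mixed model on actual days since injury, in place of raw change from Contact 1 by visit alone. Section 12.2 already names linear mixed models, though for other types of outcome. Show Contact 1 values by day band, for example 0–3, 4–7 and 8–14 days.
2. **Draw promptly and align the text.** State that Contact 1 blood is taken as soon as consent or the consultee declaration is signed, even if the visual tests follow on another day. Reconcile section 8 with the inpatient approach and the sampling of unconscious patients in section 5.

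**Cost.** Two time fields, partly covered by existing records, about one degree of freedom for a linear term, and a wording change. No extra samples are needed. Blood and visual tests may fall on different days. Prompt drawing does not close the window, because enrolment itself may occur as late as day 14, so the second step does not replace the first. With about 24 to 30 acute patients the adjustment will be imprecise, which is why the values by day band should be shown as well.

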6.2 Schedule of Assessments and Risks

Screening/enrolment

Study name:	y name: Traumatic brain injury related changes in military veterans						
Protocol version number:	3.0	version date:	11 October 2023	Page:	15 of 22		

Patients' eligibility and willingness to participate will be assessed as described above in the section on consent.

Clinical assessments (Contact 1-6)

All participants recruited will undergo collection of blood and saliva to detect fluid biomarkers of injury, visual function assessments, mental health status and PROMs. Assessments at the 12 month point will be conducted face to face where possible, but where patients are unable to attend (e.g. have moved away) will be conducted remotely. Study time points for visits 2-6 will allow a 10% variation from stated timings. Face to face visits will therefore be at enrolment, 1 month (acute TBI only), 6 months (all patients) and 12 months (acute TBI and veterans where possible).

Taking blood using a needle is uncomfortable, can cause bruising and bleeding and sometimes fainting. Only trained staff will collect the blood samples to ensure this does not occur. Saliva will be collected in a tube and is not invasive and should not cause any problems.

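### Acute TBI group: Contacts 2–5 may be timed from injury or from enrolment, so the 1-month contact can fall on days 27–47 after injury instead of days 27–33

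*Protocol*

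**What the plan says.** Figure 2 (section 6.1) applies to the acute TBI group only. It gives three timing rules:

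- First contact: "Contact 1 (0-14 days post head injury or at enrolment".
- Middle contacts: "Contact 2-5 (1, 3, 6 and 9 months after head injury or enrolment".
- Close-out: "Contact 6 (12 months after head injury".

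Section 6.2 adds the window: "Study time points for visits 2-6 will allow a 10% variation from stated timings". It does not say from which origin the timing is counted.

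The gap between the two origins is bounded by how patients enter. Inclusion criterion 5 in section 4.1 reads "Moderate or severe head injury requiring admission to the Queen Elizabeth Hospital within the prior 14 days", and section 5 (Consent) has patients approached after "head injury for the acute TBI group (i.e. 0-14 days post-injury".

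The 1-month contact is substantial. Figure 2 puts blood and saliva there ("X (1 and 6 months only, face to face"), together with SOFAS, the self-reported measures and visual function. Section 6.2 confirms the attendance: "Face to face visits will therefore be at enrolment, 1 month (acute TBI only), 6 months (all patients". On vision the protocol disagrees with itself. A later paragraph of section 6.2 places visual testing at Contacts 1 and 3 and, where possible, Contact 6, and Contact 3 is the 3-month contact in this group.

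**The concern.** A visit window means something only if the point it is counted from is fixed. Here a patient enrolled on day 10 and seen on day 40 after injury is exactly on time by the enrolment clock and 7 days late (40 − 33) by the injury clock. Site staff cannot tell whether that visit is a deviation. Nor can *or enrolment* be explained as wording meant for veterans, who have their own enrolment-based schedule in Figure 3.

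Section 12.2 compares Contact 1 with Contacts 2–6, using repeated measures ANOVA for the continuous outcomes. That method treats a contact number as a common occasion. Section 1.2.2 hopes to learn how long after a TBI mental health and quality-of-life problems appear, which is a question about time since injury. SOFAS and the self-reported measures feed the primary outcome in section 12.1, and the fluid biomarkers are secondary. With 30 patients planned per group, and 24 with complete data assumed in section 12.2, spread in the time axis that a wording choice could remove is worth removing.

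**Working it through.** The protocol states no figure to reproduce. The check is date arithmetic.

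**Inputs**
- Entry 0–14 days after injury (sections 4.1 and 5).
- Nominal contacts at 1, 3, 6, 9 and 12 months (Figure 2).
- Window of 10% (section 6.2), read as ±10% of the nominal time.
- Length of a month: not stated. 30 days is assumed here and varied below.

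**Formulas**, in days since injury, with d the nominal time in days:
- Injury clock: 0.9d to 1.1d.
- Enrolment clock, enrolled on day 14: 14 + 0.9d to 14 + 1.1d.
- Either clock allowed, enrolment on days 0–14: 0.9d to 14 + 1.1d.

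| Contact | Nominal day | ± window | Injury clock | Enrolment clock, enrolled day 14 | Either clock | 14 days as share of nominal |
|---|---|---|---|---|---|---|
| 2 (1 month) | 30 | 3 | 27–33 | 41–47 | 27–47 | 47% |
| 3 (3 months) | 90 | 9 | 81–99 | 95–113 | 81–113 | 16% |
| 4 (6 months) | 180 | 18 | 162–198 | 176–212 | 162–212 | 8% |
| 5 (9 months) | 270 | 27 | 243–297 | 257–311 | 243–311 | 5% |

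**1 month.** The span is 47 − 27 = 20 days, against 33 − 27 = 6 days on one injury clock. Stepping through enrolment days 0 to 14 shows that every day from 27 to 47 can occur across patients. A single patient enrolled on day 14 has two separate windows, days 27–33 and 41–47.

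**Shift against window.** The 14-day shift exceeds the window at 1 month (14 > 3) and at 3 months (14 > 9). It is smaller at 6 months (14 < 18) and at 9 months (14 < 27).

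**Sensitivity to month length at 1 month, either clock.** 28 days gives 25.2–44.8; 30.44 days gives 27.4–47.5; 31 days gives 27.9–48.1. The limits move by about 2 days at most.

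**Do contacts run into each other?** Contact 1 falls on days 0–14. Contact 6, at 360 ± 36, falls on days 324–396. In order, the ranges are 0–14, 27–47, 81–113, 162–212, 243–311 and 324–396. None overlap.

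**Which single origin?** Enrolment alone would end the ambiguity, but across patients enrolled on days 0–14 the 1-month contact would still fall on days 27–47 after injury. Injury alone gives days 27–33.

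**Interval from Contact 1 to Contact 2, with Contact 1 at enrolment.** On the enrolment clock it is 27–33 days for everyone. On the injury clock it runs from 27 − 14 = 13 to 33 − 0 = 33 days.

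**The case against.** The strongest reply is that a single injury clock moves the spread elsewhere. Section 12.2 compares Contact 1 with later contacts, and Contact 1 itself falls anywhere in days 0–14. With the injury clock the Contact 1-to-2 interval varies by 20 days (13 to 33), as much as the spread complained of; with the enrolment clock it is 27–33 days for all. This stands as a genuine trade-off. Two things favour injury: Contact 6 already uses it, and the aim in section 1.2.2 is framed as time after TBI. Analysing on actual days since injury then takes the unequal intervals into account.

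Second, the dates should be recoverable. Section 9.1 keeps a record of visits and tests, with dated results where possible, and the choice of time variable is commonly left to a statistical analysis plan, so its absence from the protocol is no fault. This is accepted. But analysis cannot move visits that were already booked on different clocks, and the origin is a scheduling rule that the protocol itself leaves open.

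Third, Figure 2 heads the Contact 2–5 column with a note that the monitoring interval is set clinically. That weakens any inference about how tight the timing was meant to be. It does not choose an origin, and it fits poorly with a fixed 10% window.

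Stronger readings that a reader might infer are not supported:
- **Patients at the same time since injury could be booked at different contacts.** The ranges do not overlap, so at most one patient is at a contact while another is between contacts.
- **The spread is a bias linked to severity.** That would need sicker patients to enrol later. The protocol gives no such evidence, and section 5 has a consultee route for unconscious patients.
- **The whole follow-up is compromised.** At 6 and 9 months the shift lies inside the window. The interval from Contact 5 to Contact 6 can shrink from 90 to 76 days (360 − 284) for a day-14 enroller on the enrolment clock, but Contact 6 has its own window of ±36 days.

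**Conclusion.** The point holds, at modest size. The acute group's Contacts 2–5 have two permitted origins and no rule for choosing, while Contact 6 has one. The consequence is a 20-day range of compliant dates at 1 month where the injury clock gives 6, and a 32-day range at 3 months (113 − 81) where it gives 18 (99 − 81). It also leaves a 10% window that cannot be applied unambiguously.

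Assumptions and limits:
- The month is taken as 30 days and the window as ±10% of nominal time.
- The ranges are limits, not expected spread. The upper ends need enrolment on day 14 and use of the enrolment clock.
- The 14-day gap follows from the entry windows. Criterion 5 could be read as dating the admission, and enrolment could follow the approach by some days, so the gap could be somewhat larger.
- For blood, saliva, SOFAS and self-reported measures the 1-month conclusion is secure. For vision it depends on Figure 2 being right; the conflict with section 6.2 is a separate matter to reconcile.

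**What to change.** In Figure 2, delete *or enrolment* from the timing of Contacts 2–5, so that they are counted from the date of head injury as Contact 6 already is. Keep the 10% window. Analyse the acute group with actual days since injury as the time variable, including at Contact 1, for example in a linear mixed model in place of nominal contact number in a repeated measures ANOVA.

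The cost is a small wording change and an earlier second contact for late enrollers: a patient enrolled on day 14 has a nominal gap of 30 − 14 = 16 days before Contact 2. The variation in that gap enters the within-patient change from Contact 1, so the wording change and the actual-time analysis should be adopted together. The spread of Contact 1 over days 0–14 remains; the analysis can account for it but the schedule does not remove it.
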